11.6 Neurophysiology

Repetitive nerve stimulation (RNS) is performed at baseline and after 24 weeks for centers where neurophysiology is located locally.

Surface electrodes are applied to a muscle, the muscle nerve is stimulated with a series of electric shocks at rest, after maximum activation of the muscle, 1 min and 3 min after activation and the amplitude is measured.

RNS is performed in the proximal arm muscle (deltoid) and facial muscle (nasalis) and measures disturbed neuromuscular transmission by measuring decrements.

The patient should not take cholinesterase inhibitors within 12 hours before the examination.

- RNS procedure:
 - o Low-frequency nerve stimulation (3 Hz) 10 times at rest
 - o Muscle activation 20 seconds and then again 3 Hz stimulation 10 times
 - o 1 minute after activation again low-frequency nerve stimulation (3 Hz) 10 times
 - o 3 minutes after activation again low-frequency nerve stimulation (3 Hz) 10 times
- Measurement parameters:
 - o% amplitude decrement (reduction) between 1st and 4th muscle response (compound motor action potential; CMAP)
 - o% area decrement between 1st and 4th CMAP
 - o CMAP amplitude in absolute numbers at rest (mV)

The examination is performed at a neurophysiological lab at each hospital. Patients admitted to centers that do not have a neurophysiological lab in the hospital do not need to do this test.

11.7 Adverse Event, AE and Serious Adverse Event, SAE.

Follow-up regarding AE and SAE will be carried out during the telephone follow-ups and all physical visits that the patient carries out at the center.

The patient is informed at the start of the study to contact the center if new or worsening symptoms should arise. If symptoms worsen significantly, or if the patient experiences an MG crisis (difficulty breathing), the patient should inform the physician and make an evaluation visit as soon as possible or no later than 48 hours after the onset of symptoms. Treatment of the patient then takes place in accordance with standard care for the patient's clinic or hospital.

12 Management of adverse events

As a reference safety information for assessing whether an adverse event is expected or not, Mabthera SmPC / SmPC will be used.

12.1 Definitions

12.1.1 Adverse events (AE)

Any adverse medical event or deterioration of an existing medical condition, whether related to treatment or not.

12.1.2 Serious adverse events (SAE)

Any accidental medical event occurring at any dose:

- · results in death
- is life threatening
- causes hospital stay or extended hospital stay (see also section 12.5 regarding hospitalization for MG relapses)
- results in permanent or temporary disability
- results in a congenital injury / malformation
- a medically important event that involves danger to the patient or that could have resulted in any of the above if not taken care of

12.1.3 Suspected, unexpected, serious adverse events (SUSAR)

A reaction / event that is unexpected, serious, suspected to be caused by the treatment and that has not been described before.

12.2 Assessement of adverse events

12.2.1 Assessement of seriousness

Any adverse medical event should be classified by the examiner as mild, moderate, or severe.

Mild: The event does not affect the person's normal life.

Moderate: The event causes deterioration of function but does not affect health. The event causes discomfort and / or discomfort / obstacles.

Severe: The event causes impairment of function or ability to work or poses a health risk to the person.

12.2.2 Assessement of causality

Related / probably related: Clinical event, including abnormal laboratory analyzes, which occur within a reasonable time after administration of the intervention / study product. It is unlikely that the event can be attributed to the underlying disease or other drugs.

Possibly related: Clinical event, including laboratory analyzes, occurring within a reasonable time after administration of the intervention / study product. The event can also be explained by the underlying disease or other drugs.

Not related: Clinical event, including abnormal laboratory analyzes, which may be temporarily related to the administration of the intervention / study product. The event is unlikely to be related to the intervention / study product and may better be explained by other drugs or underlying disease.

12.3 Methods for detection of adverse events

At the start of the study, the patient is informed to contact the center in the event of new or worsening symptoms. During telephone follow-ups and return visits that the patient carries out at the clinic, the patient will also be asked if any unwanted medical events have occurred since the last time.

Protocoll nr: 2015-00887 Date: 2021-04-26 Version 7.0 (ENG)

n 7.0 (ENG) 25(42)

12.4 Reporting of adverse events

12.4.1 Reporting of adverse events (AE)

All adverse medical events are noted in a special AE form, where the severity is assessed as severe or non-serious.

12.4.2 Reporting of serious adverse events (SAE)

Serious adverse events should be reported to the sponsor on a special SAE form within 24 hours of the study center becoming aware of the SAE.

Follow-up information describing the outcome and management of SAE should be reported as soon as that information is available. The original report must be inserted in the investigator binder.

12.4.3 Reporting of suspected, unexpected, serious adverse events (SUSAR)

The sponsor is responsible for all relevant information about suspicious, unforeseen, serious adverse reactions being registered and reported to the EudraVigilance database.

SUSARs that are fatal or life-threatening are reported to the EudraVigilance database as soon as possible and no later than 7 days after the occurrence has become known to the sponsor. Relevant follow-up information must then be submitted within a further 8 days. Other SUSARs are reported as soon as possible and no later than within 15 days after they have come to the sponsor's notice.

Information about SUSAR that occurs during the study will be compiled by the sponsor and sent out to the principal examiner at all participating centers quarterly in the form of a CIOMS form.

12.5 Follow up of adverse events

Adverse Event, AE

AE that occurs after the study drug has been administered until the visit week 48 will be documented, summarized, and analyzed in the study. If treatment is needed, this is done in accordance with the protocol and based on the medical assessment of the treating physician.

AE that is judged to be caused by the underlying disease or previously known diseases will not be registered as AE in the study. Should the underlying disease worsen during the study, this may be considered an AE.

AEs will be followed up until they are "resolved" or until the patient's participation in the study is completed.

Serious Adverse Event, SAE

SAE that arises from the start of administration of study drugs until the patient ends his / her participation in the study will be documented and reported, as well as summarized and analyzed after the study.

Planned hospitalization / surgery for illness or condition that the patient had before the start of the study will not be registered as SAE.

Note that hospitalization that is primarily caused by exacerbated MG symptoms (MG crisis) should not be considered SAE. If the deterioration and hospitalization are secondary to, for example, pneumonia, the event must be reported as SAE.

SAEs will be followed up until they are "resolved" or until the patient's participation in the study is completed.

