9.2 Exclusion criteria

- 1. Weakness affecting only ocular or periocular muscles (MGFA class I).
- 2. MG crisis at screening (MGFA class V).
- 3. Thymectomy already performed. To avoid difficulties in evaluating the effect of the study drug, thymectomy, in cases where it is deemed indicated, should be planned for the follow-up period, i.e. only after the first 24 weeks.
- 4. Strong suspicion of thymoma and where thymectomy according to the treating physician should be performed within 24 weeks.
- 5. Activecancer, unless adequately treated.
- 6. Pregnancy or breast-feeding.
- 7. Any ongoing acute or chronic viral or systemic bacterial infection including HIV, latent hepatitis B, which is clinically significant in the opinion of the study physician, and which has not been treated with appropriate antibiotic / antiviral drugs.
- 8. Severe heart failure (New York Heart Association Class IV) or severe uncontrolled heart disease
- 9. Previous use of immunosuppressive drugs including rituximab, azathioprine, ciclosporin and MMF. The use of Prednisolone at a dose of ≤40mg / d within 3 months and IVIG and PLEX 12 months from the screening date does not constitute an exclusion criterion. Please also note that this does not apply to treatment with immunosuppressive drugs / corticosteroids (excluding rituximab) for indications other than MG, provided that > 12 months have elapsed since the end of treatment.
- 10. Hypersensitivity to the active substance, to murine proteins or to any of the other excipients in the study medicinal product
- 11. Participation in any other clinical drug study or exposure to any other study drug, study product or study procedures within 30 days before screening.
- 12. Any medical condition which, in the opinion of the study physician, may interfere with the patient's participation in the study, poses any additional risk to the patient, or which complicates the assessment of the patients.

Protocoll nr: 2015-00887 Date: 2021-04-26

Version 7.0 (ENG) 19(42)

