15.3 Benefit risk assessement

During the study, blood samples will be taken and an intravenous catheter inserted for the administration of study drugs. For most patients, the placement of intravenous catheters and needle punctures for blood sampling is well tolerated. In rare situations, however, they can cause bleeding, bruising, swelling, coagulation in the vein, leakage of medication or solution into the surrounding tissues, and possibly infection at the site of insertion of the needle or catheter. Sampling and insertion of an intravenous catheter will be performed according to clinical practice by staff with extensive experience in this field.

As with all medicines, rituximab can cause side effects, although well tolerated compared to other biological medicines. The side effects of rituximab are usually mild or moderate. The investigator will discuss possible side effects with the patient and explain the risks and benefits of rituximab before treatment. Because rituximab is being studied in MG patients, not all possible side effects are known.

Very common side effects (affects at least 1 in 10 patients) include fever, itching, redness of the skin, nausea, headache.

Common side effects (affects 1 or more in 100 patients and less than 10 in 100 patients) include: reduced platelet count, abdominal pain, constipation, vomiting, diarrhea, stomach discomfort after meals, nausea, chest discomfort, chills, infusion-related reaction, anaphylactic reaction, edema, fever, tiredness, weakness, cold sores, cold, viral infection, stomach flu, bronchitis, severe infection, muscle aches, back and neck pain, pain in limbs and joints, muscle cramps, dizziness, disturbances in taste, tingling of the body, vertigo, high blood pressure, difficulty or pain when urinating, spontaneous erection, upper respiratory tract infection, pneumonia, urinary tract infection, joint infection, cough, irritation or pain in the throat, nasal congestion, itchy skin, rash, hair loss, and dry skin.

In addition, serious infections, sepsis, and infusion reactions have been reported in patients receiving rituximab and these are identified safety hazards.

Patients receiving rituximab will have a weakened immune system, which may affect the patient's ability to fight viral and bacterial infections. Patients treated with rituximab have an increased risk of worsening certain chronic infections, such as hepatitis B.

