Based on what has been described above, the risks that study participation entails are considered acceptable given that the study population includes patients with new-onset moderate to severe MG (moderate to severe effects on ADL), which is a condition that risks deteriorating further if immunomodulatory treatment is not instituted, in turn involving other types of risks such as osteoporosis, poor blood sugar control and other side effects of cortisone.

The patient's condition may improve, remain the same, or worsen during the study. If the study and possibly other studies with rituximab in MG are positive, this may lead to benefit for other patients, as clinical evidence for efficacy with this drug is then substantiated. It is worth mentioning that today there is a complete lack of approved treatments for MG and that clinical practice is based entirely on proven experience. We believe that this will affect national practice for the treatment of MG.

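### Section 12.5 bars registration of adverse events blamed on previously known diseases, against 12.1.1 and 12.4.1, so non-serious worsening of non-MG conditions may be captured incompletely or differently between sites

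*Combined protocol and SAP*

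**What the plan says.** Four parts of the combined protocol and SAP decide what reaches the AE form.

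- **Definition, 12.1.1.** An AE is: "Any adverse medical event or deterioration of an existing medical condition, whether related to treatment or not".
- **Reporting, 12.4.1.** "All adverse medical events are noted in a special AE form", with no exception stated there.
- **Causality, 12.2.2.** Each event is graded as related or probably related, possibly related, or not related. The possibly related category covers events of which it says: "The event can also be explained by the underlying disease or other drugs".
- **Follow-up, 12.5.** AEs from study drug administration to the week 48 visit are to be documented, summarised and analysed. The section then adds: "AE that is judged to be caused by the underlying disease or previously known diseases will not be registered as AE in the study". The next sentence reads: "Should the underlying disease worsen during the study, this may be considered an AE".

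Serious events have their own paragraph in 12.5. It leaves out only planned admissions or surgery for conditions present before the study, and admissions caused primarily by worsened MG.

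Safety is part of the study objective (Summary, 8.1), and adverse events are listed among the tertiary and explorative endpoints in 7.3.

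**The concern.** Section 12.5 uses an opinion on cause to decide whether an event is recorded at all. The usual order, and the one 12.2.2 presupposes, is to record the event and then grade its cause. One site cannot tell from one patient whether a drug has made a known condition worse. Only recorded events, compared between arms, can show an excess.

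The harm most exposed is one the protocol itself names. Section 15.3 warns: "Patients treated with rituximab have an increased risk of worsening certain chronic infections, such as hepatitis B". In a patient with a known infection, such a worsening is easily put down to the old disease, and 12.5 then tells the site not to register it.

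At stake is the completeness of the non-serious safety data, and whether the same event is handled alike across the 10 to 15 planned centres.

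**Working it through.** No arithmetic decides this point, and the plan has no figure of its own to reproduce. The check is to trace one kind of event through the rules: a non-serious worsening, after dosing, of a non-MG condition the patient already had.

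1. **Is it an AE by definition?** Under 12.1.1, yes. Deterioration of an existing condition is included, and relation to treatment is irrelevant.
2. **Does it go on the form?** Under 12.4.1, yes, because all adverse medical events do.
3. **Is there a place to record the site's view of cause?** Yes. In 12.2.2 the possibly related category covers events that the underlying disease could also explain, and the not related category covers events better explained by it. Both presuppose that the event has been recorded.
4. **Does 12.5 register it?** Not if the site judges the known disease to be the cause. Steps 1 and 2 cannot then be followed together with 12.5.
5. **Does the exception for worsening rescue it?** On the natural reading, no. The preceding sentence lists the underlying disease and previously known diseases as two separate things, and the exception repeats only the first. Even for MG it is permissive.
6. **Would the event be caught as serious?** Not in this example, since it is non-serious. An unplanned serious worsening of a non-MG condition would still be reported, because the SAE exclusions are limited to planned admissions or surgery and MG admissions.
7. **Can a patient with a known chronic infection be enrolled?** Yes. Exclusion criterion 7 in 9.2 applies to an infection that is clinically significant in the study physician's opinion and "which has not been treated with appropriate antibiotic / antiviral drugs". A treated or not clinically significant infection can therefore enter.
8. **Is there another planned route?** Only in part. Section 11.1 ties the routine panel (including liver enzymes, CRP, glucose and hepatitis B screening) to screening. The week 16 and 24 samples described in 8.5 are serum for exploratory immunology. Somatic status and concomitant medication are checked later, but they are not a register of events.

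The outcome depends on which section a site follows. If all follow 12.5, these events are missing. If all follow 12.1.1 and 12.4.1, they are kept. If practice is mixed, capture differs by site.

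**Direction of any effect between arms.** Suppose the true rates of such events are p1 and p0, and a share f is filtered out in both arms alike. The observed difference is (1 − f)(p1 − p0). Equal filtering under blinding does not create a false excess, but it shrinks a real one. The documents give no value for f, p1 or p0.

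**The case against.** The strongest reply is that loss is not certain. Sections 12.1.1 and 12.4.1 both point towards registration, and a site may well follow them. That stands, and it is why the conclusion is incomplete or inconsistent capture rather than certain loss.

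Several stronger readings are tempting, and the documents do not support them.

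- **A formal safety comparison is damaged.** Section 13.2 specifies no test of adverse events, and they are a tertiary or explorative endpoint. What suffers is the summary and analysis that 12.5 promises.
- **Chronic infection flares vanish generally.** The case is narrow. Hepatitis B is screened, criterion 7 keeps out significant untreated infection, a flare attributed to study drug is registered, and a medically important one is an SAE. What remains is a non-serious flare that the site blames on the old infection.
- **Worse glucose in a known diabetic is removed.** Section 15.3 lists "poor blood sugar control and other side effects of cortisone" among the risks of other treatment. A site that attributes the event to cortisone has not judged diabetes to be its cause, so 12.5 does not exclude it. It is lost only if the cause is misattributed.
- **The loss can be counted.** With 47 patients, or about 24 per arm, one patient moves an arm's AE incidence by 1/24, or 4.2 percentage points, but only if the unregistered event was that patient's only one. Multiplying 47 by assumed shares with comorbidity and with worsening counts a different group, because it includes patients with other registered events. The documents supply neither share.

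It can also be said that the exception for worsening might be read loosely, as covering any pre-existing disease. The wording makes that the less natural reading, and the exception would still be discretionary.

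**Conclusion.** The contradiction is real. Section 12.5 excludes from registration events that 12.1.1 and 12.4.1 include, and its exception does not reach non-MG conditions. Where sites follow 12.5, non-serious worsening of those conditions is filtered by a judgement on cause before it is recorded.

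The scope is limited. Serious events other than planned and MG admissions, events attributed to study drug, and the primary endpoint are not affected. The size cannot be derived, because the documents give no AE rates, no comorbidity counts and no record of which rule sites applied.

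The conclusion rests on two readings: that the underlying disease in 12.5 means MG, and that criterion 7 excludes only infections that are both clinically significant and untreated. Correction is worthwhile because safety is a stated objective and the remedy is small.

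**What to change.** Reconcile 12.5 with 12.1.1 and 12.4.1:

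- Delete the reference to previously known diseases from the exclusion sentence in 12.5.
- Register any new event, and any worsening of a pre-existing non-MG condition, from study drug administration to week 48, which is the window 12.5 already uses.
- Record the suspected cause under 12.2.2, after registration.
- Leave out only pre-existing conditions that are unchanged from baseline.

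Version 7.0 is dated 2021-04-26, while the Summary plans the study period to end in Q1 2021. On that timetable a change of wording alone recovers nothing. Unregistered events should therefore also be sought in the source records (14.1 lists the medical record and the paper CRF as source data). Failing that, the AE summary should state which rule sites applied and that non-serious worsening of known conditions may be under-recorded.

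The cost is one sentence in 12.5 and slightly more AE forms or, at this stage, a source-record check.

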12.6 Annual safety reporting (Development Safety Update Report, DSUR)

During the study, an annual safety report (DSUR) will be sent to the Medical Products Agency and the Regional Ethics Review Board.

The report contains a summary of the SAEs and SUSARs that have occurred, a summary assessment of the safety of the patients included in the study and information on the benefit-risk assessment has changed since the study was approved.

Protocoll nr: 2015-00887 Date: 2021-04-26 Version 7.0 (ENG)

on 7.0 (ENG) 26(42)

13 Statistics, data handling and archiving

13.1 Deciding on number of study subjects

Based on results reported in Sanders DB et al.², our own experience, and a shorter phasing out of cortisone than used in most protocols, it is estimated that \leq 40% in the placebo group achieve the primary endpoint of a daily Prednisolone dose \leq 10mg with QMG \leq 4. With 25 patients in each arm, the power will be 0.85 with an alpha = 0.05 for a two-sided test of 80% reaching the primary endpoint of the active arm.

[Note, due to slow recruitment the funder of the study, the Swedish MRC, requested a revised power calculation. March 15th 2018 the following text was submitted, which was approved May 25th 2018:

"The study regards a study drug being administered on only one occasion, with determination of main endpoints at 4 and 6 months, respectively. Possible drop-outs are therefore limited to study participants actively interrupting the study, including the follow-up visits that the protocol stipulates, or that dies before these visits. Of a total of 23 included study participants, none have interrupted. One study participant died due to a medical condition not considered directly related to the study medication. A revised power calculation with the same input variables (without loss) shows that with the same number of patents in each treatment arm: 20 per arm (N = 40), power = 81%; 22.5 per arm (N = 45), power = 85%; 25 per arm (N = 50), power = 89%. Based on interim results, it is therefore reasonable to expect a dropout rate <5%. In order to maintain a power of at least 80% and a certain margin for any minor imbalance in the randomization, n≥45 is needed." The power calculation provided in the paper is based on this revised calculation.]

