- 7. Patients must be able and willing to follow all study procedures.

Exclusion criteria

Weakness affecting only ocular or periocular muscles (MGFA class I).

- 2. MG crisis at screening (MGFA class V)
- 3. Thymectomy already performed. To avoid difficulties in evaluating the effect of the study drug, thymectomy, in cases where it is deemed indicated, should be planned for the follow-up period, i.e. only after the first 24 weeks.
- 4. Strong suspicion of thymoma and where thymectomy according to the treating physician should be performed within 24 weeks.
- 5. Active cancer, unless adequately treated
- 6. Pregnancy or breast-feeding.
- 7. Any ongoing acute or chronic viral or systemic bacterial infection including HIV and latent hepatitis B, which is clinically significant in the opinion of the study physician, and which has not been treated with appropriate antibiotic / antiviral drugs.
- 8. Severe heart failure (New York Heart Association Class IV) or severe uncontrolled heart disease
- 9. Previous use of immunosuppressive drugs including rituximab, azathioprine, ciclosporin and MMF. The use of Prednisolone at a dose of ≤40mg / d within 3 months and IVIG and PLEX 12 months from the screening date does not constitute an exclusion criterion. Note that this does not apply to treatment with immunosuppressive drugs / corticosteroids (excluding rituximab) for indications other than MG, provided that> 12 months have elapsed since the end of treatment.
- 10. Hypersensitivity to the active substance, to murine proteins or to any of the other excipients in the study medicinal product11. Participation in any other clinical drug
- study or exposure to any other study drug,

study product or study procedures within 30 days before screening.

12. Any medical condition which, in the opinion of the study physician, may interfere with the patient's participation in the study, poses any additional risk to the patient, or which complicates the assessment of the patients.

13. Vaccination within 4 weeks before inclusion

TIDSPLAN

Study period: Q4 2016 – Q1 2021

Recruitment period: Q4 2016 – Q1 2020

Protocoll nr: 2015-00887

Date: 2021-04-26

Version 7.0 (ENG)

2 Abbreviations

Förkortning	Förklaring
AE	Adverse Event
APL	Apotek Produktion & Laboratorier AB
CMM	Center for Molecular Medicine
DSUR	Development Safety Update Report
EQ5D	EuroQol 5-dimensions
GCP	Good Clinical Practice
ICH	International Conference on Harmonisation
IV	Intravenous

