In the largest randomized study to date in MG, in which 176 patients with persistent symptoms were randomized 1: 1 to mycophenolate or placebo, the active arm showed no significant improvement over placebo over 6 months on the primary endpoint; the proportion of patients with minimal symptoms and a daily dose of prednisolone \leq 10 mg per day (44% in active arm versus 39% in placebo)². In another study, 80 patients with mild to moderate generalized AChR-positive MG and a daily dose of 20 mg Prednisolone were randomized to MMF and placebo, respectively, and followed for 12 weeks with MMF. The primary efficacy parameter was change in the quantitative MG (QMG) scale³, which did not differ significantly between the study arms (p = 0.71)⁴. These study results show that a significant proportion of MG patients continue to have generalized weakness involving limb weakness and bulbar symptoms (difficulty chewing, swallowing, speaking, and breathing) despite adequate dosing of immunosuppressive therapy. There is thus a great need to test newer treatment algorithms, which may include more effective biological drugs.

Several minor observational studies have shown that rituximab, an anti-CD20 monoclonal antibody that eliminates B cells, may have beneficial effects in treatment-refractory MG. There are currently a couple of randomized drug trials with rituximab using a haematological treatment protocol with repeated dosing of the drug for several weeks, with a total dose of over 2,000 mg. At Karolinska University Hospital, in recent years, more than 30 patients with MG, both refractory and new-onset patients, have been treated with rituximab, with a single infusion of 500 mg with good results and without serious side effects. In some cases, the treatment has been repeated after 6-12 months. An interesting observation is that the effect of the treatment seems to come much earlier than traditional immunosuppressive drugs, which leads to a reduced risk of hospitalizations and exposure to unnecessarily high cortisone doses. These experiences warrant further investigation of the efficacy and safety of rituximab in newly-diagnosed MG patients with moderate-to-severe disease and a low-dose protocol. The same dose (500 mg) is used by us for multiple sclerosis, where we currently have about 500 patients under treatment at Karolinska University Hospital.

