13.2 Analysis plan

Differences in the primary endpoint will be tested on an intention-to-treat basis using Fisher's exact test. As a secondary analysis, the primary endpoint will also be analyzed with log-binomial regression, adjusted for any observed baseline differences that have occurred despite randomization.

Patients who have received disease-modulating MG treatment as indicated in section 10.7 as "Not allowed" after randomization and before the assessment visit at 16 weeks will be counted as non-responders.

In addition to the primary efficacy variable, a few secondary outcome measures of particular clinical relevance have been selected to reduce the risk of false-positive findings. Differences in the change of these continuous measures will be tested with the Mann-Whitney U-test. P-values will be adjusted with Bonferroni correction for these three tests. To estimate 95% confidence intervals around the difference, linear regression with robust standard errors will be used, without adjustment for the number of tests. Patients who have received disease-modulating MG therapy as indicated in section 10.7 as "Not allowed" after randomization and before the assessment visits at 16 and 24 weeks will be censored from the time these treatments were administered.

A challenge in clinical trials is the management of dropouts, which risks introducing a selection error if response data are only available to the patients who remain in the study. As this study only involves study drug administration at baseline, we expect that the drop-out rate, and thus the need for imputation for those who have left the study, will be limited. If the dropout rate is higher than 10%, imputation will be performed, partly with multiple imputation with explicit modeling of the treatment outcome as a function of baseline variables (age, gender, disease activity), partly through so-called "last observation carried forward", where values for patients who left the study are replaced with their most recently observed value. However, it is very important to emphasize the

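### The powers quoted in 13.1 are not those of the Fisher's exact test planned in 13.2; at 80% vs 40%, N = 45 gives 75.1–76.9%, not 85%

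*Combined protocol and SAP*

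**What the plan says.** Section 13.1 sets the planning values. At most "40% in the placebo group achieve the primary endpoint", and the power is for "80% reaching the primary endpoint of the active arm", with two-sided alpha 0.05. The 2018 revision for the funder keeps these inputs, assumes no loss, and gives "20 per arm (N = 40), power = 81%; 22.5 per arm (N = 45), power = 85" per cent, then 89% at 25 per arm. It concludes: "In order to maintain a power of at least 80% and a certain margin for any minor imbalance in the randomization, n≥45 is needed". No test or formula is named. The section ends: "The power calculation provided in the paper is based on this revised calculation".

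Section 13.2 names the test: "Differences in the primary endpoint will be tested on an intention-to-treat basis using Fisher"'s exact test. The Summary gives the study size as N=47. For context, section 5.1 cites an earlier mycophenolate trial with a similar responder endpoint: "44% in active arm versus 39% in placebo".

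**The concern.** A power figure describes a particular test. Fisher's exact test is conservative in samples this small, so a normal approximation without continuity correction overstates its power. If the 2018 figures come from such an approximation, the claim that 45 patients secure 80% power does not apply to the analysis that will be done.

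The stake is how the result is read. Readers use the planned power to judge a null or borderline finding. At N = 45 the quoted type II error is 15%; if the planned test has less power, the chance of missing the assumed effect is larger than stated, and 13.1 says the paper's power statement rests on these figures.

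**Working it through.** **Inputs.** Active rate 0.80, placebo rate 0.40, two-sided alpha 0.05, no loss (13.1); 1:1 allocation (8.1); Fisher's exact test (13.2); N = 47 (Summary). Arm sizes below are active/placebo.

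**Step 1: reproduce the plan's figures.** The unpooled normal approximation is

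power = Φ( |p1 − p2| / √(p1q1/n1 + p2q2/n2) − 1.96 ), with p1q1 = 0.16 and p2q2 = 0.24.

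- 20 per arm: SE = √(0.40/20) = 0.1414; 0.40/0.1414 = 2.828; Φ(0.868) = 80.7% (stated 81%).
- 22.5 per arm: SE = √(0.40/22.5) = 0.1333; ratio 3.000; Φ(1.040) = 85.1% (stated 85%).
- 25 per arm: SE = √(0.40/25) = 0.1265; ratio 3.162; Φ(1.202) = 88.5% (stated 89%).

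All three agree to rounding. Other usual formulas do not: the version with pooled variance under the null gives 75.2%, 80.3% and 84.5%, and the arcsine version 76.2%, 80.9% and 84.8%. The source is therefore inferred from the match; 13.1 does not state it.

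**Step 2: power of the planned test.** For each pair of arm sizes, list every 2×2 table, compute the usual two-sided Fisher p-value, keep the tables with p ≤ 0.05, and sum their probabilities under Bin(n active, 0.80) × Bin(n placebo, 0.40).

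| N | Arms | Fisher power | Stated in 13.1 |
|---|---|---|---|
| 40 | 20/20 | 65.0% | 81% |
| 45 | 22/23; 23/22 | 75.1%; 76.9% | 85% |
| 46 | 23/23 | 72.7% | – |
| 47 | 23/24; 24/23 | 78.2%; 79.9% | – |
| 48 | 24/24 | 76.0% | – |
| 49 | 24/25; 25/24 | 80.8%; 82.5% | – |
| 50 | 25/25 | 78.8% | 89% |

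The stated values exceed the Fisher values by about 16 points at N = 40, 8–10 at N = 45 and 10 at N = 50. Power is saw-toothed in N because the test is discrete. With arms as equal as possible, N = 49 is the only size from 45 to 50 that reaches 80%. The conservatism shows in the size of the test: over all common response rates, the largest type I error is 3.7% at 22/23 and 4.0% at 23/24.

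**Step 3: the margin for imbalance.** At N = 45, 21/24 gives 73.6% and 24/21 gives 76.5%. No split from 19/26 to 26/19 reaches 80%. Even the pooled normal approximation gives only 80.2–80.4% at 22/23 and 23/22, so the margin exists only under the unpooled formula.

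**Step 4: sensitivity to the placebo rate** (active 80%, near-equal arms).

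| Placebo rate | N = 45 | N = 47 |
|---|---|---|
| 40% | 75.1–76.9% | 78.2–79.9% |
| 39% | 77.4–79.0% | 80.4–81.9% |
| 37% | 81.6–82.9% | 84.3–85.5% |
| 35% | 85.3–86.3% | 87.8–88.7% |

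**The case against.** The strongest reply is that the shortfall is small where it counts. The study size is 47, not 45. Near-equal arms there fall short of 80% by 0.1–1.8 points, and a 25/22 split reaches 80.1%. Section 13.1 also gives 40% as an upper limit; at 37% placebo response, N = 45 with near-equal arms already passes 80%. Finally, the 2018 text is a quoted submission that the funder approved. It records how the trial was sized, and according to the Summary ("Recruitment period: Q4 2016 – Q1 2020") recruitment was to have ended before this version, dated 2021-04-26.

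Much of this stands. It limits the consequence and rules out any design change. It does not rescue the printed figures. The plan computed 81%, 85% and 89% at 40%, and at 40% the planned test does not have those powers. The stated threshold is 45, and at 39%, the placebo rate cited in 5.1, N = 45 still gives less than 80%. For N = 47 the plan prints no power; the formula that matches its other figures would give 86.4–86.7%, 6.5–8.5 points above Fisher's test. That no formula is named affects only the explanation of the gap, not the gap.

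**Conclusion.** The concern holds. At the plan's own inputs, Fisher's exact test has 75.1–76.9% power at N = 45 against the stated 85%, a type II error of 23–25% instead of 15%. At N = 47 the type II error is 20–22%. The statement that 45 patients keep at least 80% with a margin for imbalance is wrong at 40% placebo response.

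This rests on an active rate of 80%, the usual two-sided Fisher p-value and no loss. It is specific to placebo rates near 40%: with near-equal arms the shortfall at N = 47 has gone at 39%, and at N = 45 it has gone at 37%. The type I error, the validity of Fisher's test, the endpoint and the sample size are unaffected. It should be fixed as a matter of reporting.

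**What to change.** Leave Fisher's test, the sample size and the quoted 2018 text as they are. After that text in 13.1, add a note such as:

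> The powers quoted above are consistent with a normal approximation. For the Fisher's exact test in 13.2 (80% vs 40%, two-sided alpha 0.05, no loss; active/placebo), exact power is 65.0% at N = 40 (20/20), 75.1–76.9% at N = 45 (22/23, 23/22), 72.7% at N = 46 (23/23), 78.2–79.9% at N = 47 (23/24, 24/23) and 78.8% at N = 50 (25/25). A total of 45 or more does not secure 80% power at 40% placebo response. At N = 47 and 39% placebo response, power is 80.4–81.9%.

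A line with the 35% placebo values (85.3–86.3% at N = 45) would show how quickly the shortfall disappears. Wherever the trial's power is reported, give the Fisher power for the actual N and arm sizes in place of the 2018 figures. If those are also shown, label them as the basis on which N was chosen.

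The cost is one note and a matching power statement. Nothing changes for patients, endpoint, test or sample size. The only drawback is that the stated power becomes less favourable.
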